5.1 Study Design

This is an open-label pilot clinical trial prospective study of treating patients with relapsed/refractory DLBCL or relapsed/refractory follicular lymphoma with duvelisib at a dose of 25 mg p.o. b.i.d. for 8 to 15 days prior to collection of mononuclear cells by apheresis for the purpose of CAR-T manufacturing. The intended duration of duvelisib exposure is 2 weeks. The duration of duvelisib may be adjusted to a period between 8 and 15 days depending upon the schedule of apheresis, with the last dose of duvelisib on the day of apheresis.

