7.1 Apheresis Collection

Patients will need to undergo leukapheresis within two (2) days of completion of the 8 to 15 day treatment of duvelisib. Apheresis will be performed at the Emory Center for Transplantation and Cell Therapy. Peripheral blood mononuclear cells will be collected for CAR-T cell manufacturing according to the standard of care. A single 2-4-hour leukapheresis will be performed on the COBE Optia with the intention of harvesting 3×10^9 white blood cells. If patients are unable to collect the necessary amount required for manufacturing, they can undergo a second leukapheresis. If patients are not able to collect enough product after the second leukapheresis, they will be considered unevaluable and replaced. After apheresis, the quantity of CD27/CD28 double positive T cells, CD4/CD8 double negative gamma delta positive T cells and CD4/CD8 double negative gamma delta negative T cells will be measured via flow cytometry. CAR-T cell manufacturing will be provided by Novartis and are expected to be ready 4 weeks after collection. Failure of the incoming apheresis material or outgoing product to meet the commercial specifications will be discussed with Novartis on a case by case basis.

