17.5.1 Study Design Endpoints

This is pilot study to examine if exposure to a dual PI3K delta and gamma inhibitor before CAR T cell leukapheresis leads to decreases in manufacturing time and enhanced expression of CD27/CD28+ T cells. Patients who receive at least 75% (23/28 doses) of duvelisib will be evaluable for final analysis. Patients who do not receive 75% of doses will be considered unevaluable and replaced. Patients who do not undergo leukapheresis within two (2) days of completion of the 8 to 15 days of duvelisib will be considered unevaluable and replaced. All patients with any exposure to duvelisib will be evaluable for toxicity (please see section 13.3 on grading of toxicities).

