17.5.2 Analysis of Primary Endpoints

All patients that complete >75% of planned duvelisib doses and undergo leukapheresis within 2 weeks of duvelisib treatment completion will be included in the final analysis of the primary endpoint. The primary endpoint of the study to estimate the fold-change increase in CD27/CD28 double positive T cells following *in vivo* exposure to duvelisib from baseline to day 15. Our in vitro studies have shown that culturing DLBCL patients' T cells with 14 days of duvelisib increased the amount of CD27/CD28 double positive T cells from 12.2% to 32.7% (Petersen, et al, supplemental data). However, there are currently no *in vivo* background data to benchmark the expected fold-change CD27/CD28 double positive T cells over a 14-day window. Therefore, with 20 patients, this pilot study will be based on estimation on the fold change increase only and will not include a formal evaluation of the change against a null unpromising fold-change. However, we will consider this study promising if there is at least a two-fold increase in CD27+/CD28+ in at least 75% of patients.

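### Sections 17.5.1 and 17.5.2 define the primary analysis set differently on both the leukapheresis window and the dose rule, so the denominator of the two-fold/75% benchmark is not fixed

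*Combined protocol and SAP*

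**What the plan says.** All of the following is current text in the combined protocol and SAP.

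- **Window in 17.5.1 and 7.1.** Section 17.5.1: "Patients who do not undergo leukapheresis within two (2) days of completion of the 8 to 15 days of duvelisib will be considered unevaluable", with replacement. Section 7.1: "Patients will need to undergo leukapheresis within two (2) days of completion of the 8 to 15 day treatment of duvelisib". Section 5.1 describes a course of 8 to 15 days, intended to be 2 weeks, "with the last dose of duvelisib on the day of apheresis".
- **Window in 17.5.2.** Patients with enough doses who "undergo leukapheresis within 2 weeks of duvelisib treatment completion will be included in the final analysis of the primary endpoint".
- **Dose in 17.5.1.** The minimum is 75%, glossed as 23 of 28 doses (5.7 repeats the gloss). "Patients who do not receive 75% of doses will be considered unevaluable and replaced".
- **Dose in 17.5.2.** More than 75% of planned doses. The word planned is not defined.
- **Low yield, 7.1.** "If patients are not able to collect enough product after the second leukapheresis, they will be considered unevaluable and replaced".
- **Early stop, 5.3.** A patient taken off duvelisib for an adverse event does not restart it but may still have leukapheresis at the scheduled time.
- **Benchmark, 17.5.2.** The plan says that "this pilot study will be based on estimation on the fold change increase only", and then that "we will consider this study promising if there is at least a two-fold increase in CD27+/CD28+ in at least 75% of patients". The denominator is not named; its placement implies the primary analysis set.
- **All exposed patients.** Section 17.5.1 assigns them to the toxicity evaluation. No version of the two-fold result is planned for them.

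**The concern.** A patient collected on days 3 to 14 after finishing duvelisib is replaced under 17.5.1 and analysed under 17.5.2. A patient who takes every dose of a permitted 10-day course fails a 23-dose rule and passes a percentage-of-planned rule. Nothing says which section governs.

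The two-fold/75% benchmark is the only threshold set for the primary endpoint. If the definition is settled after the flow cytometry results are known, the choice of denominator becomes data-dependent. Some excluded patients may also have both samples: phenotyping is done at screening and before apheresis (5.7), and patients stopped for an adverse event may still be collected. Completion (17.5.3 item 1) and discontinuation for adverse events (17.5.5) will be reported, so a reader could bound the two-fold rate among everyone who started duvelisib but could not see it.

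**Working it through.** **1. The benchmark as a count.** The sample size of 20 has no stated derivation, so there is no design figure to reproduce. The benchmark is 0.75 × 20 = 15 patients. The exact (Clopper-Pearson) 95% interval for 15/20 is 50.9% to 91.3%.

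**2. The window.** Two days (17.5.1, 7.1) against 14 days (17.5.2). The disputed band is days 3 to 14.

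**3. The dose rule.** 23/28 = 82.1%, whereas 0.75 × 28 = 21. At two doses a day:

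| Course (days) | Doses available | 75% of these, rounded up | Can reach 23? |
|---|---|---|---|
| 8 | 16 | 12 | no |
| 10 | 20 | 15 | no |
| 11 | 22 | 17 | no |
| 12 | 24 | 18 | yes, with 23/24 = 96% |
| 14 | 28 | 21 | yes |
| 15 | 30 | 23 | yes |

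Three patients show how the rules part:

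- 20 of 20 doses on a 10-day course: fails 23 doses. Passes 17.5.2 if planned means the patient's own course (100%), but fails if it means 28 (20/28 = 71%).
- 22 of 28 doses (78.6%): meets 75%, fails 23 doses, passes 17.5.2.
- 21 of 28 doses (exactly 75%): meets the 75% wording of 17.5.1, fails its 23-dose gloss, and fails the strict inequality in 17.5.2.

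**4. Effect on the benchmark.** Suppose 20 patients are evaluable under 17.5.1, s of them reach two-fold, and r disputed patients are added under 17.5.2. The proportion lies between s/(20 + r), if none of the added patients reaches two-fold, and (s + r)/(20 + r), if all do.

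- s = 15, r = 1: 15/21 = 71.4% to 16/21 = 76.2%.
- s = 15, r = 2: 15/22 = 68.2% to 17/22 = 77.3%.

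The smallest r that takes the result below 75% in the worst case:

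| s of 20 | r | Result |
|---|---|---|
| 15 | 1 | 15/21 = 71.4% |
| 16 | 2 | 16/22 = 72.7% |
| 17 | 3 | 17/23 = 73.9% |
| 18 | 5 | 18/25 = 72.0% |

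A patient at exactly 75% of doses could move the other way, in under the 75% wording and out under the strict inequality. From 15/20, removing one gives 14/19 = 73.7% or 15/19 = 78.9%.

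**5. Early stop with collection on schedule.** 23 doses take 23/2 = 11.5 days, so the last falls on about day 12. Collection on day 15 is then three days later. This patient meets even the 23-dose rule. The two-day window is missed if completion means the last dose taken, and met if it means the end of the scheduled course. The text does not say which.

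**The case against.** The strongest reply has four parts.

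*The 2-week wording is a slip with little reach.* Section 7.1 requires collection within two days and 5.1 puts the last dose on the day of apheresis, so for a fully dosed patient a later collection would already be a deviation. This largely stands and limits the size of the point. It does not reach the dose rule, which affects patients following a permitted short course.

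*Two days is not plainly the better window.* The 2-week wording would keep the patient in step 5. This stands: choosing two days without defining completion could drop patients whom 5.3 allows to be collected on schedule.

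*An evaluable set suits the question.* Asking whether adequate exposure shifts T-cell phenotype, in adequately exposed patients with replacements, is coherent for an estimation-only pilot. This stands, and the evaluable set should remain primary.

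*The movement is within noise.* 71% against 75% is small beside an interval of 50.9% to 91.3%. True, but the benchmark is applied to the point estimate, so the label can change even though the evidence barely does.

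A reader might infer more than the documents support:

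- *That replacement biases the study toward being called promising.* The ranges in step 4 lie on both sides of 75%, so the direction is unknown.
- *That up to ten treated patients will be replaced, because section 12 expects 30 consents for 20 patients.* Section 12 does not separate screen failures from replacements. Dosing is short, and the median onsets quoted in 4.2.4 are later (1.2 months for AST/ALT elevation, 2.2 to 4 months for diarrhea).
- *That 17.5.2 brings low-yield patients into the primary set.* This requires reading it in isolation from the explicit exclusion in 7.1.
- *That the Wilcoxon test in 17.5.3 has no population.* The general evaluability rule in 17.5.1 reasonably covers it.

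**Conclusion.** The point holds as an inconsistency in the definition of the primary analysis set, on the window and on the dose rule together. Correcting the window alone would leave the set defined two ways. In the most fragile case, 15/20, one disputed patient decides whether the benchmark is met (71% or 76%); at 18/20 it would take five added patients, none reaching two-fold.

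These figures assume twice-daily dosing throughout, 20 patients evaluable under 17.5.1, and disputed patients with paired samples counted in addition. How many there will be is not stated and may be few. The benchmark is descriptive and nothing is triggered by it, so the consequence is an ambiguous label, not a wrong decision. The correction should be made before results are seen. The call for a result in all dosed patients holds only as a supportive analysis; the documents give no ground for replacing the evaluable set.

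**What to change.** 1. Use one definition in 17.5.1 and 17.5.2: at least 75% of the doses planned for that patient's own 8- to 15-day course, and leukapheresis within two days of completion. Delete the 23/28 gloss, including in 5.7.
2. Define completion, and state whether a patient stopped early for an adverse event but collected on schedule under 5.3 meets the window.
3. Keep the low-yield exclusion in 7.1, and keep the evaluable set as primary.
4. Add one supportive table: the proportion reaching two-fold, with an exact 95% interval, among all patients who took at least one dose and have paired samples, including late-collected, low-yield and adverse-event-stopped patients. List replacements by reason. Counting missing samples as not reaching two-fold is optional, because it mixes attrition with biology.
5. State in advance that a differing supportive result is reported as such and does not override the primary result.

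The cost is a short wording change and one table from samples already scheduled. The downside is that the figure for all dosed patients may be less favourable than the primary one.

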17.5.2 Analysis of Primary Endpoints

All patients that complete >75% of planned duvelisib doses and undergo leukapheresis within 2 weeks of duvelisib treatment completion will be included in the final analysis of the primary endpoint. The primary endpoint of the study to estimate the fold-change increase in CD27/CD28 double positive T cells following *in vivo* exposure to duvelisib from baseline to day 15. Our in vitro studies have shown that culturing DLBCL patients' T cells with 14 days of duvelisib increased the amount of CD27/CD28 double positive T cells from 12.2% to 32.7% (Petersen, et al, supplemental data). However, there are currently no *in vivo* background data to benchmark the expected fold-change CD27/CD28 double positive T cells over a 14-day window. Therefore, with 20 patients, this pilot study will be based on estimation on the fold change increase only and will not include a formal evaluation of the change against a null unpromising fold-change. However, we will consider this study promising if there is at least a two-fold increase in CD27+/CD28+ in at least 75% of patients.

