1.1 Synopsis

This pilot study will evaluate a 8 to 15 day exposure to duvelisib in patients with relapsed/refractory Diffuse Large B Cell Lymphoma (DLBCL) or follicular lymphoma prior to undergoing apheresis of a mononuclear cell product for the purpose of CAR-T manufacturing. The primary objective of the study is to determine whether the immune profile of T cells can be favorably changed by short-term exposure to duvelisib prior to collection of mononuclear cells for CAR-T 19 cell manufacturing. Secondary objectives include feasibility of adherence to duvelisib for 8 to 15 day, assessment of manufacturing time of patients, assessment of proportions of CD27/CD28 T cells and CD4/CD8 double negative Gamma Delta T cells to historical controls, comparison of rates cytokine release syndrome (CRS)neurotoxicity or ICU transfer and overall response rate (ORR) at 90 days. The study will also determine if a 8 to 15 day exposure to duvelisib is safe and well tolerated in this setting.

Title:	Duvelisib Exposure to Enhance Immune Profiles of T Cells in Patients with Diffuse Large B Cell Lymphoma (DEEP T CELLS)
Study Description:	
This Pilot study will evaluate whether an 8 to 15 day exposure to Duvelisib will favorably change the immune profile of T cells prior to CAR-T 19 cell manufacturing. We hypothesize that short term exposure to Duvelisib will:
 
increase frequencies of CD27/28 double positive naïve and memory T cells.increase frequencies of CD8+CD45RO-CD27+ T cells.increase frequencies of CD4/CD8 double negative Gamma Delta T cells.
Objectives:	
Primary Objective:
 
To assess changes in T cell phenotype after 8 to 15 day exposure to duvelisib prior to collection of mononuclear cells for CAR-T cell manufacturing. 
Secondary Objectives:
 
To evaluate compliance with duvelisibTo evaluate the CAR-T 19 manufacturing timeTo describe frequencies of CD27/28 double positive T cells and CD4/8 double negative T cellsTo evaluate expansion and persistence of CAR-T cellsTo evaluate overall response rates following CAR-T cell therapyTo evaluate survival rates following CAR-T cell therapyTo describe the frequency of CRS and neurotoxicity requiring ICU transfer (for CRS or neurotoxicity) and/or treatmentDescribe the safety and tolerability profile of duvelisib

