1.2 Schema

Days -14 to 0	Screening
	
• Total n= 20• Obtain informed consent• Screen potential participants by inclusion and exclusion criteria• Obtain history, document
Day 1	Follow-up assessments of study endpoints and safety Baseline assessments/ Study Intervention
	
• Administer initial dose of Duvelisib
	Refer to Section 1.3, Schedule of Activities
Day 8	
	
• Refer to Section 1.3, Schedule of Activities
Day 15	
	
• Refer to Section 1.3, Schedule of Activities
CART-T Day 0-90	Post CAR-T 19 Infusion Assessments
	
• Refer to Section 1.3, Schedule of Activities

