1.3 Schedule of Assessments

Table 1: Pre and During Study Assessments on duvelisib (Day 1= First day of duvelisib)

Procedures and Tests	Days -14 to 0	Day 8 +/-1	Day 15 +/-2
Medical History	X		
Physical Exam	X	X	X
Performance Status	X	X	X
Vital Signs	X	X	X
Labs: [*]	X	X	X
CBC	X	X	X
CMP	X	X	X
TSH	X		
Magnesium	X		
Phosphorous	X	X	X
HIV Ag/Ab	X		
Hepatitis Serologies	X		
Covid-19 PCR (-7 to 0)	X		
EKG	X		
Immunophenotyping of T-Cells	X		X
PET/CT [*]	X		
Serum or Urine Pregnancy Test ^{**}	X		
Adverse Events		X	X

* Standard-of-care

** Standard-of-care. Also see section 11.1 regarding risk to fetus and requirement for contraception while on study

Table 2: Post CAR-T 19 Cell Infusion Assessments (post-hospital discharge, will be captured with chart review) (CAR-T Day 0 (cD0)= Date of CAR-T infusion)

Procedures and Tests	Day 7 +/-1 (post CAR-T)	Day 14 +/-2 (post CAR-T)	Day 28 +/-2 (post CAR-T)	Day 42 +/-3 (post CAR-T)	Day 90 +/-3 (post CAR-T)
CAR-T 19 PCR [*]	X	X	X	X	X
Immunophenotype of CAR-T [*]	X	X	X	X	X
PET/CT or CT [*]					X

* Standard-of-care

2. Objectives (and Endpoints)

OBJECTIVES	ENDPOINTS
Primary	
1. To assess the increase in CD27+/CD28+ T cells, after 8 to 15 day exposure duvelisib prior to collection of mononuclear cells for CAR-T cell manufacturing.	1. The fold change increase in proportion of T cell phenotypes co-expressing CD27/28 using multiparametric flow cytometry.
Secondary	

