Leukocyte immunophenotyping (via flow cytometry/fluorescence-activated cell sorting) will be done at screening and prior to apheresis for manufacturing CAR-T cells. This will determine the amount of B/T/NK cells and more specifically, the phenotypes and frequencies pre and post Duvelisib exposure.

Electrocardiogram

All ECG's will use a 12-lead tracing and performed during screening only. ECG will measure PR interval, QRS interval, RR interval and QTc. Additional ECG's and other cardiac tests can be performed as clinically indicated.

6. Data and Specimen Banking

Blood samples will be obtained and used for medical research by the investigators of this study. *Data and specimens from this study may be useful for other research being done by investigators at Emory or elsewhere. To help further science, Investigators may provide de-identified data and/or specimens to other researchers. Any information that could identify patients will not be included. If data or specimens are labeled with study ID, we will not allow other investigators to link that ID to identifiable information.*

Samples and data collected under this protocol may be used to study lymphoma. Access to stored samples will be limited to IRB-approved investigators. Samples and data will be stored using codes assigned by the investigators or their designees. Data will be kept in password-protected computers. Only investigators will have access to the samples and data.

All stored samples will be maintained in the laboratory to which it was sent initially for analysis. Study patients who request destruction of samples will be notified of compliance with such request and all supporting details will be maintained for tracking.

The results of some study tests and procedures will be used only for research purposes and will not be placed in patient's medical record. For this study, those items include: research blood collection.

7. Tisagenlecleucel Apheresis Phase

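### The primary post-duvelisib value is fixed at Day 15, which for short permitted courses falls after cell collection, while section 5.7 places the draw before apheresis

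*Combined protocol and SAP*

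**What the plan says.** **Post value at Day 15.** Section 17.5.2 defines the primary fold change over "exposure to duvelisib from baseline to day 15". Item 3 of 17.5.3 uses the same two time points for the signed-rank test. The treatment-phase list in 5.6 has phenotyping on Days 1 and 15 only. In Table 1 (section 1.3) the row "Immunophenotyping of T-Cells" is marked at screening and at Day 15 ±2, not at Day 8.

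**Post value before apheresis.** Section 5.7 says that leukocyte immunophenotyping "will be done at screening and prior to apheresis for manufacturing CAR-T cells". The primary objective reads "To assess changes in T cell phenotype after 8 to 15 day exposure to duvelisib prior to collection of mononuclear cells" in the synopsis, with near-identical wording in section 2.

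**Course length and apheresis.** Section 5.1 states "The intended duration of duvelisib exposure is 2 weeks", then allows 8 to 15 days to suit the apheresis schedule, "with the last dose of duvelisib on the day of apheresis". Sections 7.1 and 17.5.1 allow apheresis up to two days after the course ends; 17.5.2 says two weeks.

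**Who is analysed.** Section 17.5.1 requires at least 75% of doses, which it writes as 23 of 28; 5.7 gives the same figure. Section 17.5.2 requires more than 75% of planned doses.

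**Baseline.** Table 1 and 5.7 give a screening draw. Section 5.6 gives screening and Day 1. Section 17.5.2 does not say which is used.

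**The concern.** Day 15 suits a two-week course. Once the course may be as short as 8 days and apheresis follows at once, a calendar anchor can fall after the event it is meant to precede. A site following 17.5.2 and Table 1 would then phenotype blood after the manufacturing cells had been taken and after duvelisib had stopped, whereas 5.7 asks for a sample before collection. Section 7.2 also permits bridging chemotherapy after apheresis, so such a sample could follow that as well.

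What is at stake is which quantity the trial estimates. There is no formal test, so power and type I error are not in question. The study is called promising if at least 75% of patients show a two-fold increase. With 20 patients that is 0.75 × 20 = 15, and each patient whose status changes moves the proportion by 1/20 = 5 percentage points.

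**Working it through.** The plan states no figure to reproduce; the check is a count of days.

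**Inputs.** Day 1 is the first dose (Table 1), so a course of L days ends on Day L, with L = 8 to 15 (5.1). Apheresis is on Day L + k: k = 0 under 5.1, k = 0 to 2 under 7.1 and 17.5.1. The draw window is Day 13 to 17. Dosing is twice daily, so a course has at most 2L doses.

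**Step 1: when is the whole window after collection?** When 13 > L + k.

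| Apheresis after last dose | Condition | Whole window after collection | Both rules can be met |
|---|---|---|---|
| same day (k = 0) | L < 13 | 8–12 days | 13–15 days |
| 1 day (k = 1) | L < 12 | 8–11 days | 12–15 days |
| 2 days (k = 2) | L < 11 | 8–10 days | 11–15 days |

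From k = 5 no course is affected (8 + 5 = 13), but only the two-week limit in 17.5.2 would allow that delay.

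**Step 2: how long off drug?** The draw falls 13 − L to 17 − L days after the last dose, whatever the apheresis date: 5 to 9 days for L = 8 and 1 to 5 days for L = 12.

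**Step 3: which affected courses enter the analysis?** Maximum doses are 16, 18, 20 and 22 for L = 8 to 11, and 24, 26, 28 and 30 for L = 12 to 15. The plan's 23/28 is 82%; 75% of 28 is 21.

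| Dose rule | Courses that can qualify | Affected, k = 0 | k = 1 | k = 2 |
|---|---|---|---|---|
| 23 doses, literal | 12–15 | 12 | none | none |
| 21 doses (75% of 28) | 11–15 | 11–12 | 11 | none |
| more than 75% of the patient's own planned course (assumed meaning of 17.5.2) | 8–15 | 8–12 | 8–11 | 8–10 |

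**Step 4: baseline.** A screening draw may be as early as Day −14, so it and a Day 1 draw can be up to 1 − (−14) = 15 days apart. That is the extreme, not an expectation.

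**The case against.** The best defence is that Day 15 is only a label for the end-of-treatment visit. Table 1 is headed as covering assessments on duvelisib, the intended course is two weeks, the synopsis endpoint refers only to 8 to 15 days of exposure, and 5.7 puts the draw before apheresis. A site reading these together might well sample at the right moment. This is good evidence of intent, and the label may simply have been kept when the exposure range was widened (an inference). It does not remove the rule: 17.5.2, 17.5.3(3), 5.6 and Table 1 all say Day 15, and an analyst following them would use a post-collection value.

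It is also fair that the certain conflict may be small. Under a literal 23 doses it shrinks to one course length with same-day apheresis, and the documents give no expected number of short courses.

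A reader might take the primary objective itself to require a draw before collection. It is consistent with that, but "after 8 to 15 day exposure duvelisib prior to collection of mononuclear cells" can equally describe when the exposure happens. Section 5.7 is the unambiguous passage.

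A reader might also infer that the baseline is wrong unless taken on Day 1, because a screening sample could follow chemotherapy closely. The documents do not support going that far. Section 11.2 excludes chemotherapy within two weeks before study entry. The schema's Day 1 row, "Baseline assessments/ Study Intervention", appears to be merged text and is weak evidence. Appendix D refers to a sampling schema not shown in this copy, which may settle the matter.

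The flow measurement in 7.1 after apheresis does not rescue the primary value either, since 17.5.2 does not refer to it.

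**Conclusion.** The inconsistency stands, and it concerns the primary endpoint: for some permitted courses no draw can satisfy both 17.5.2 and 5.7. The affected range is 8–12 days with same-day apheresis, 8–11 with apheresis one day later and 8–10 with it two days later. Courses of 13–15 days can comply with both, although Table 1 does not require the draw to precede collection even then: with same-day apheresis, nominal Day 15 is one day after collection for a 14-day course.

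The number of patients ranges from possibly none to every short course, depending on which dose and apheresis rules govern. The widest range assumes that planned doses means the patient's own course.

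It would be tempting to conclude that the primary estimate is biased, or biased downward because the drug has worn off. The documents give no in vivo data on how CD27/CD28 expression changes after the last dose, so neither the size nor the direction can be stated. What can be said is that an affected value is off drug and post-collection, and that compliant readings of the plan could give different primary results. The undefined baseline is a secondary point.

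**What to change.** - In 17.5.2 and 17.5.3(3), replace Day 15 with the peripheral-blood draw taken before apheresis at the end of dosing, whatever the calendar day.
- Align Table 1 and 5.6 with 5.7.
- Report each fold change with the actual exposure days and the days from last dose to draw.
- Flag any patient with only a post-collection draw, and show the primary result with and without such patients.
- State in 17.5.2 which existing draw is the baseline, and check it against the Appendix D schema. Either draw can serve if it is named in advance.
- The sponsor must reconcile the passages on apheresis timing (5.1; 7.1 and 17.5.1; 17.5.2) and on dose evaluability (17.5.1; 17.5.2). I do not say which is right.

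The cost is wording. The post draw moves rather than being added, and both baseline candidates are already listed in 5.6. The drawback is a pre/post interval that follows the course length. From a Day 1 baseline it is L − 1 = 7 to 14 days with same-day apheresis, or L + 2 − 1 = 9 to 16 days with apheresis two days later. Reporting exposure days makes that visible. A missed pre-apheresis sample cannot be recovered, so the change is best made before further patients are collected.
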